8.4 Inclusion and exclusion criteria

Inclusion criteria: 1. Patients admitted to the Centro Medico ISSEMYM Toluca Arturo Montiel Rojas, diagnosed with COVID-19. 2. Patients in need of supplemental O₂ with nasal prongs or mask-reservoir due to satO₂ <90% and respiratory distress. 3. With concomitant diseases such as cardiovascular disease, diabetes mellitus 2, hypertension, overweight or obesity BMI <35. 4. 5. Over 30 years of age. 6. Tolerant of oral feeding. 7. Signed informed consent letter.

Non-inclusion criteria: 1. Who requires mechanical ventilatory support. 2. 2. Present neurological or neurodevelopmental disorders. Severe gastroesophageal reflux and/or dysphagia. 4. 4. Patients with any type of surgery performed in a period of less than 3 months. 5. Allergies to any ingredient of the study treatment. 6. Who present acute malnutrition. 7. Patients who require admission to the Intensive Care Unit. 8. Who has criteria of sepsis or septic shock. 9. Glomerular filtration rate less than 60ml/min/1.73m².

Criteria for elimination: 1. Treatment failure. 2. Admission to ICU for any reason. 3. Patients who do not tolerate the oral route. 4. Reactions to treatment that compromise the health of the patients.

Sampling and allocation: Consecutive cases. Systematic randomized allocation by means of a sequence of random numbers constructed with the Excel program divided into two groups.

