A handwritten signature in black ink, appearing to be '[name]', written over a horizontal line. The signature is stylized with loops and a long vertical stroke at the end.

6. Roles and Responsibility - signatures

Names	Roles and Responsibility	Signature
[name] M.D., MSc., DSc.	Conceptualization, formal analysis, funding acquisition, investigation, methodology, project administration, supervision, writing-review, and editing.	
[name] M.D., MSc., DSc.	Formal analysis, funding acquisition, review, and editing.	
[name] M.D.	Data curation, formal analysis, investigation, methodology, project administration resources, writing-review, and editing.	
[name] M.D.	Data curation, formal analysis, investigation, methodology, project administration resources, writing-review, and editing.	
[name] M.D.	Data curation, investigation, methodology, project administration resources, writing-review, and editing.	

[name]	Data curation, formal analysis, investigation, methodology, writing-review, and editing.	
[name] M.D	Hospital Resources.	

Section 2: INTRODUCTION

7. Background and rationale of study (optional)

Item 7: Synopsis of trial background and rationale including brief description of research question and brief justification for undertaking the trial

COVID-19 is a rapidly spreading disease with a high hospital mortality rate. It has caused the collapse of health systems worldwide due to the lack of specific treatments to reduce complications and mortality. Nutrition has only been considered as an energetic support even though malnutrition has been associated with a higher risk of mortality. Therefore, it is important to investigate a nutritional support system that helps to reduce mortality and increase survival in patients with COVID-19 in stage III and comorbidities to a greater degree than with conventional nutritional treatment.

8. Objectives and hypotheses.

Item 8: Description of specific objectives or hypotheses

The primary objective is to determine the effectiveness of the Nutritional Support System (NSS) on increasing survival and reducing mortality in patients with COVID-19 in stage III and comorbidities compared to conventional nutritional therapy.

Secondary objectives:

1. To evaluate the effect of the NSS on progression to intubation, evolution to extubation, and mortality in intubated patients.

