Item 13b: Any planned adjustment of the significance level due to interim analysis:

No adjustment of the significant level due to interim analysis are planned.

13c. Details of guidelines for stopping a trial early:

The following points are considered in planning the early stopping of the study:

1. That the intervention causes serious adverse effects in patients generating insecurity in its application.
2. That the investigators detect improbable, ineffective, or extreme differences between the CG and the IG.

3. New information emerges that raises serious safety issues or convincingly answers to the main question.

14. Timing of final analysis

Item 14: Timing of final analysis e.g all outcome analyzed collectively or timing stratified by planned length of follow-up

The follow-up will start in September 2020 until the established sample is met.

The last day of the study for each patient is going to be 40 days after hospital discharge.

Statistical analysis of clinical and biochemical variables will be performed on baseline, day three, hospital discharge and day 40. Analysis of overall survival and mortality will be performed from baseline to day 40 or patient death. Progression of patients to Mechanical Ventilation Assistance (MVA) will be performed from baseline until the last patient is intubated, mortality in patients with MVA will be performed from intubation to day 40 or death.

15. Timing of outcome assessments

Item 15: Time points at which the outcomes are measured

Survival and Mortality

- Overall survival and mortality: performed from baseline to day 40 or patient death.
- Progression of patients to Mechanical Ventilation Assistance (MVA): performed from baseline until the last patient is intubated.
- Mortality in patients with MVA: performed from intubation to day 40 or death.

Clinical and biochemical variables

- Delivered oxygen flow and maintenance of SpO₂ > 90%: will be analyzed at baseline and day three.
- qSOFA scale: will be analyzed at baseline compared with day three.

- Gastrointestinal function (average of gastrointestinal movements, abdominal distension, and Bristol scale): will be analyzed at baseline compared with day three.
- Laboratory parameters: will be analyzed at baseline, day three and hospital discharge.
- PHQ-9: will be analyzed at baseline and hospital discharge.

Follow-up at day 40

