Categorical data will be summarized by numbers and percentages. Normality tests will be applied to evaluate the distribution of the data. If the continuous data present a normal distribution, they will be assumed by mean, SD, and range. If they do not present a normal distribution, they will be summarized with the median and the IQR. Minimum and maximum values will also be presented for continuous data. Statistical significance tests will be performed between both groups in the baseline to rule out significant differences.

Section 6: Analysis

26. Outcomes definitions

Item 26a: Specification of outcomes and timings

Primary outcomes

- Overall mortality and survival will be assessed from the baseline to day 40.
- Progression to AVM will be assessed from baseline until the last patient is intubated.
- Mortality and survival in intubated patients will be assessed from baseline to day 40.

These results will be included in the results section of the manuscript.

Secondary Outcomes

Administration of supplemental oxygen flow, oxygen saturation (spO₂), qSOFA scale, and gastrointestinal function will be assessed by comparing at baseline to day 3 intragroup and intergroup. The PHQ-9 test will be assessed at baseline and at discharge between both groups.

These results will be included in the secondary outcomes section of the manuscript. Analysis of the association of baseline biochemical parameters and mortality will be considered in a table and in the secondary outcomes section of the manuscript.

The spO₂ without supplemental oxygen requirement, home supplemental oxygen requirement, post COVID syndrome, and body weight at day 40 will be analyzed between both groups in a table.

These results are included in the follow-up section of the manuscript.

Item 26b: Specific measurement and units

- SpO₂ (%)
- Mortality (days of death)
- Kilocalories (kcal / day)
- PHQ9 (pts).
- Temperature (°C).
- Hemoglobin (g / dL).
- Mean corpuscular volume (fL).
- Mean corpuscular hemoglobin concentration (g / dL).
- Leukocytes ($10^3 / \mu\text{L}$).
- Neutrophils (%).
- Platelets ($10^3 / \mu\text{L}$).
- Glucose (mg / dL).
- Total cholesterol (mg / dL).
- Triglycerides (mg / dL).
- Aspartate aminotransferase (U / L).
- Alanine aminotransferase (U / L).
- Albumin (g/dL).
- Blood Urea Nitrogen (mg / dL).
- Urea (mg / dL).
- Creatinine (mg / dL).
- Glomerular filtration rate
- Ferritin (ng / mL)
- Fibrinogen (mg / dL)
- C-reactive protein (mg / L)
- Dimer-D (ng / mL)

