- Procalcitonin (ng / mL)

27. Analysis methods

To consider statistical significance in the results, a value of $p < 0.05$ will be used.

The analysis of the primary and secondary outcomes is shown in the following table.

Variable	Outcome	Timing	Normality test	Summary results	Parametric test	Nonparametric test	Categorical data test	Analysis type
Overall survival	Primary	40 days follow-up	-	Kaplan-Meier	-	-	Log Rank	Intergruppal
Progression to intubation	Primary	until the last patient is intubated	-	Kaplan-Meier	-	-	Log Rank	Intergruppal
Survival in intubated	Primary	40 days follow-up	-	Kaplan-Meier	-	-	Log Rank	Intergruppal
Oxygen flow (L)	Secondary	Basal vs day 3	Shapiro-Wilk	Mean and SD	Paired T test	Wilcoxon	-	Intragruppal
qSOFA (pts)	Secondary	Basal vs day 3	Shapiro-Wilk	Mean and SD	Paired T test	Wilcoxon	-	Intragruppal
Defecations per day (No.)	Secondary	Day 3	Shapiro-Wilk	Mean and SD	Unpaired T test	Mann Whitney	-	Intergruppal
Distension (Yes/No)	Secondary	Day 3	Shapiro-Wilk	Proportions	-	-	Fisher	Intergruppal
PHQ-9 (pts)	Secondary	Basal vs Discharge	Shapiro-Wilk	Mean and SD	Paired T test	Wilcoxon	-	Intragruppal
Oxygen saturation >90%	Secondary	Day 3	Shapiro-Wilk	Proportion	-	-	Fisher	Intergruppal
Hydric balance	Secondary	Day 3	Shapiro-Wilk	Mean and SD	Unpaired T test	Mann Whitney	-	Intergruppal
Bristol scale "normal"	Secondary	Day 3	Shapiro-Wilk	Proportion	-	-	Fisher	Intergruppal
Saturation without supplemental O2	Secondary	Day 40	Shapiro-Wilk	Mean and SD	Unpaired T test	Mann Whitney	-	Intergruppal
Need for supplemental O2 at home	Secondary	Day 40	Shapiro-Wilk	Proportion	-	-	Fisher	Intergruppal
Days of supplemental O2 use at home	Secondary	Day 40	Shapiro-Wilk	Mean and SD	Unpaired T test	Mann Whitney	-	Intergruppal
Postcovid syndrome	Secondary	Day 40	Shapiro-Wilk	Proportion	-	-	Fisher	Intergruppal
Decrease in weight	Secondary	Day 40	Shapiro-Wilk	Proportion	-	-	Fisher	Intergruppal
Gastrointestinal symptoms	Secondary	Day 40	Shapiro-Wilk	Proportion	-	-	Fisher	Intergruppal

28. Missing data

Item 28: Missing data-reporting and assumptions/statistical methods to handle missing data

(multiple imputation)

Statistical methods to handle missing data will not be performed.

30. Harms

Item 30: Sufficient detail provided on summarizing harms

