D dimer – ng/mL	291.2 ± 179.9	444.9 ± 954.9	0.927
Creatinine – mg/dL	0.88 ± 0.31	0.86 ± 0.22	0.734
Urea – mg/dL	33.95 ± 15.84	32.95 ± 10.78	0.710
BUN – mg/dL	15.87 ± 7.39	15.43 ± 5.02	0.690
GFR – mL/min/1.73 m ²	90.15 ± 20.2	93.59 ± 17.4	0.673
Procalcitonin – ng/mL	0.364 ± 0.6	0.18 ± 0.188	0.356

The comparison of both groups in the baseline did not show a significant difference in any item analyzed in this study.

SD, Standard Deviation. CG, control group. IG, intervention group. MNA, Mini Nutritional Assessment.

Figure 2. Kaplan-Meier general survival curve from CG and IG patients

[figure not shown]

Figure 2. Kaplan-Meier general survival curve from CG and IG patients.

The proportion of patients in the IG (blue line) and the CG (red line) included in the study and completed a 40-day follow-up from September 2020 to April 2021. The cumulative proportion of surviving patients was estimated with the Kaplan-Meier method and compared in both groups, from the CG died seven of 40 patients (surveillance 82.5%, mean 36.22, 95% of confidence interval [CI] 33.46 to 38.98), otherwise from de IG died one of 40 patients (surveillance 97.5%, mean 39.31%, 95% of [CI], 37.98 to 40.64). This showed a significant difference of IG compared to CG * $p=0.027$ (Log Rank test, 95% of [CI]).

Figure 3. Kaplan-Meier survival curve from patients Receiving Mechanical Ventilation of the CG and IG.

Figure 3-A

[figure not shown]

Figure 3-B

[figure not shown]

Figure 3. Kaplan-Meier survival curve from patients Receiving Mechanical Ventilation of the CG and IG.

The proportion of patients with MVA from CG and the IG were included in the study and completed 40-day follow-up from September 2020 to April 2021. **(Figure 3-A)** IG and CG were analyzed with the Kaplan-Meier method comparing both groups to MVA progression, from CG seven patients progressed to MVA (17.5%, mean 9.68%, [IC] of 95%, 8.66 to 9.80); meanwhile, from IG three patients progressed to MVA (7.5%, mean 9.68%, [IC] of 95%, 9.34 to 10.03), this represents a 10% decrease in MVA progression of IG in comparison with CG. **(Figure 3-B)** In overall survival and mortality with MVA, five out of seven patients died in CG (71.4%, mean 19.42, [CI] of 95%, 13.09 to 25.76). One out of three patients died in IG (33.5%, mean 26.66, [IC] of 95% 11.73 to 41.6), this represents the 38.1% decrease in mortality with MVA in IG compared to CG.

Table 2-A. Clinical evolution and 40-day follow up.

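### Survival after intubation is planned as a primary between-arm log-rank test, although the intubated groups form after randomisation and the SAP disagrees with itself on the outcome's status and time origin

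*SAP*

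**What the plan says.** **Status and test.** SAP Item 26a includes this among the primary outcomes: "Mortality and survival in intubated patients will be assessed from baseline to day 40". In the Item 27 table the row "Survival in intubated" is marked primary, with Kaplan-Meier summary, log-rank test and a between-group comparison. Progression to ventilation is also primary in both places; Item 26a says "Progression to AVM will be assessed from baseline until the last patient is intubated". Item 8 instead gives, as the first secondary objective, "To evaluate the effect of the NSS on progression to intubation, evolution to extubation, and mortality in intubated patients".

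**Entry.** The first non-inclusion criterion in Protocol section 8.4 is "Who requires mechanical ventilatory support".

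**Clock.** Item 26a counts from baseline. Item 14 has "mortality in patients with MVA will be performed from intubation to day 40 or death" and Item 15 has "Mortality in patients with MVA: performed from intubation to day 40 or death". Item 14 also places each patient's last study day 40 days after discharge. Item 27 names no origin.

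**Results already printed.** The Figure 3 legend gives 7 intubated control-group (CG) patients with 5 deaths and 3 intubated intervention-group (IG) patients with 1 death, and adds "this represents the 38.1% decrease in mortality with MVA in IG compared to CG". It prints no p-value and no interval for that difference.

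**ICU.** Protocol section 8.4 lists ICU admission as a criterion for elimination, and the Procedure section ends participation at that point. The SAP follows ventilated patients to day 40.

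**The concern.** A log-rank test supports a causal reading when the groups compared are those that were randomised. Here the groups are picked by an event after randomisation that the NSS is meant to influence. If the NSS prevents some intubations, the patients still intubated in the two arms need not be alike, and a difference in their survival mixes any treatment effect with that selection. The subset also leaves out two of the seven CG deaths (7 overall, 5 after intubation).

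Followed as written, the plan would offer a non-randomised contrast in 10 patients as a primary effect of the NSS, in wording that can be taken for a relative reduction. The disagreements on status and time origin leave open how much weight the result carries and what the curve measures. A clock from baseline would also count the days before intubation, which every member of the subset survived by definition.

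**Working it through.** **Inputs** (Figure 2 and Figure 3 legends). Intubated: CG 7/40, IG 3/40. Deaths among intubated: CG 5/7, IG 1/3. All deaths: CG 7/40, IG 1/40.

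**1. The printed figure.** 5/7 - 1/3 = 0.714 - 0.333 = 0.381. So 38.1 reproduces as a difference in percentage points. (The legend prints 1/3 as 33.5%; 71.4 - 33.5 would give 37.9.) The relative reduction is 1 - (1/3)/(5/7) = 53.3%.

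**2. Precision.** Wilson limits are 0.359 to 0.918 for 5/7 and 0.061 to 0.792 for 1/3. Newcombe interval for the difference:
- lower: 0.381 - √[(0.714 - 0.359)² + (0.792 - 0.333)²] = -0.20
- upper: 0.381 + √[(0.918 - 0.714)² + (0.333 - 0.061)²] = 0.72

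Fisher's exact test, with 6 deaths in 10 patients: P(5 CG deaths) = 63/210 and P(6) = 7/210, so one-sided p = 70/210 = 0.33. Adding the equally or less likely table on the other side (35/210) gives 105/210 = 0.50 two-sided. Fisher is not the planned test; it is used because event times are not given.

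**3. What selection could do.** Assume, for illustration only, that the arms were alike at baseline and that the NSS did no more than avert 4 of 7 intubations. The fair comparator for the 3 IG patients is then the 3 CG-type patients who would still have been intubated. Removing 4 of the 7 leaves 1, 2 or 3 deaths among 3:
- all four averted would have died: 1/3 - 1/3 = 0 points
- three of the four would have died: 2/3 - 1/3 = 33 points
- two of the four would have died: 3/3 - 1/3 = 67 points

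If the four were picked at random, the probabilities are 5/35, 20/35 and 10/35, and the average is (20/35)(33.3) + (10/35)(66.7) = 38.1. Selection could therefore enlarge the difference, shrink it or leave it unchanged.

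**4. Which clock the printed means suggest.** This uses the Kaplan-Meier mean with Greenwood-type variance.
- IG: a death at 8 and a curve to 36 give 8 + (2/3)(28) = 26.67; SE = 18.67/√6 = 7.62; CI 11.73 to 41.60. Printed: 26.66 (11.73 to 41.6).
- IG from baseline: Figure 2's IG mean of 39.31 with one death implies 39 + t/40, so t is about 12.4. With a curve to 40 the mean would be 12.4 + (2/3)(27.6) = 30.8 (16.1 to 45.5), which does not match.
- CG from baseline, if both survivors were followed to day 40: 7 × 19.43 = 136 patient-days, leaving 56 for five deaths. The SE is smallest when all five fall at 11.2: SE 4.92, CI 9.8 to 29.1. The printed 13.09 to 25.76 is narrower than that.

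Both arms point to an intubation clock. They do not fix the length of the CG curve. Deaths at 9, 12, 16, 18 and 21, one survivor censored at 20 and a curve to 33 give 19.43 (13.09 to 25.76), and other combinations fit as well.

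**The case against.** **The clocks may be compatible.** Item 26a could describe an observation window and Items 14 and 15 the origin of survival time. The IG figures allow this: a death 8 days after intubation and near day 12.4 from baseline puts intubation near day 4, and a curve ending at 36 then ends at day 40 from baseline. This has force. The texts still do not say so, and Item 14's count from discharge adds a third anchor. The SAP needs one stated origin, but the documents do not show that the curve was drawn wrongly.

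**The 38.1% is labelling.** The legend prints both counts and both percentages, claims no significance for Figure 3-B, and words the progression result the same way (17.5% - 7.5% as a 10% decrease). That is fair. The sentence still attributes a decrease to groups that randomisation did not form.

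**Selection is possible, not shown.** This stands. A reader might infer that the 38.1 points are inflated in favour of the NSS. The documents give nothing on who avoided intubation, and random removal leaves the average unchanged.

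**The planned test could be kept with a caveat.** That is defensible as transparency, but a caveat does not make a 7 v 3 post-randomisation contrast a primary treatment comparison.

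**Conclusion.** The concern holds. A primary between-arm test is planned in groups formed after randomisation, and its printed result is 38.1 percentage points in 10 patients, with an interval from -20 to +72. It should not be read as an effect of the NSS. The conflict over primary or secondary status is plain from the text. The conflict over time origin is real on the page, though it may be one of drafting.

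Three stronger readings are not supported:
- *That the bias has a known direction or size.* The 0, 33 and 67 points rest on the stated assumption and only show what is possible.
- *That the printed means prove which clock was used, or how long the CG curve ran.* They suggest an intubation clock. The CG part assumes that both survivors reached day 40, and event times are not given.
- *That overall survival is either undermined or wholly safe.* The selection problem does not touch the comparison of all 80 randomised patients. The protocol's ICU rule could affect its follow-up, since five of the seven CG deaths came after intubation, but the documents do not say where patients are ventilated.

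**What to change.** 1. Report survival in the intubated as counts per arm (5/7 and 1/3), with no between-group test and no superiority claim. Keep overall mortality in all randomised patients (7/40 v 1/40) as the randomised comparison.
2. Give progression to intubation and survival after it one status each across Items 8, 26a and 27.
3. If a curve is still shown, use intubation as the time origin in Items 14, 15, 26a and 27, and state what day 40 is counted from.
4. Replace the legend's decrease sentence with the two counts and a note that these groups formed after randomisation and are not compared.
5. Record that all these changes, including the loss of primary status, were made after results were seen.
6. Reconcile the ICU provisions in Protocol section 8.4 (elimination criteria and Procedure) with SAP follow-up to day 40.

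Items 1 to 5 need only wording and counts already held. The cost is that one outcome loses its primary status and its planned test.

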2. To evaluate the effect of NSS on clinical and biochemical changes among patients.
3. To evaluate the effect of NSS on the biochemical status associated with overall mortality.

Study hypotheses

The null hypothesis: The nutritional support system will not reduce mortality or increase survival in patients with COVID-19 in stage III and comorbidities compared to conventional nutritional therapy.

Research hypothesis: The nutritional support system will reduce mortality and increase survival in patients with COVID-19 in stage III and comorbidities compared to conventional nutritional treatment.

Section 3: Trial Methods

9. Trial design - description of trial design

Item 9: Brief description of trial design including type of trial

Randomized, blinded, controlled clinical trial. Selected patients will be randomized into two groups: 1) Control Group (CG) will receive the hospital diet and 2) Intervention Group (IG) will receive the hospital diet and the NSS. Treatment allocation will have a 1:1 ratio.

10. Randomization

Randomization will be performed using a raffle; eighty numbers are to be placed (from 1 to 80). Subsequently, each number will be randomly selected from the raffle and sequentially assigned to one of the two groups, until reaching 40 numbers per group. Each number represents the moment the patient enrolls. In this way, once the recruitment starts, the first patient will be assigned number one; the second will be number two, and so on.

11. Sample size

Item 11: Full details of the same size calculation or alternatively reference to sample size calculation in protocol (instead of replication in SAP).

The sample size will be calculated using the formula: $n = \frac{z^2 p q}{e^2}$, where: 95% confidence level ($z = 1.96$), $p = 0.975$, $q = 0.025$, with a margin of error of 5% ($e = 0.05$), obtaining 38 patients per group for the sample.

12. Framework

Item 12: Superiority, equivalence or non-inferiority trial hypothesis testing framework, and wick comparisons will be presented on this basis.

The effect of NSS in increasing survival and reducing mortality in patients with COVID-19 will be demonstrated by the significant superiority of IG over CG.

13. Statistical Interim analyses and stopping guidance

Item 13a: Information on interim analyses specifying what interim analyses will be carried out and listing of time points:

No interim analyses are planned in the study.

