- SpO2 without supplemental oxygen, use of home oxygen upon hospital discharge, days of supplemental oxygen use, post-covid syndrome, decrease in body weight: all will be analyzed from hospital discharge until day 40.

Section 4: Statistical Principles

16. Confidence intervals and p-values

Item 16: Level of statistical significance

P values ≤ 0.05 will be considered indicative of statistical significance in all cases. P values will be one-sided.

Item 17: Description of any planned adjustment for multiplicity, and if so, including how the type I error is to be controlled

This study will not analyze data that required multiplicity tests. To avoid type 1 error, an alpha value of 5% will be used (considering $p < 0.05$ significant), aberrant data will be eliminated, validated tests applicable to the study variables will be defined and established, specific inclusion criteria will be implemented for homogenization of the sample to avoid bias variables, and a specific sample size calculation will be performed.

Item 18: Confidence intervals (CI) to be reported

All the confidence intervals presented will be 95%.

19. Adherence and Protocol Deviations

Item 19a: Definition of adherence to the intervention and how this is assessed including extent of exposure.

The intervention will consist of: 1) 2 envelopes of NSS taken in a period of less than 15 minutes (without the presence of vomiting) after morning and afternoon meals during the first 21 days or until hospital discharge, 2) 1 capsule of *Saccharomyces Boulardii* before the NSS and 1 capsule with the second envelope for 6 days or until hospital discharge, 3) intramuscular B complex; 1 ampoule after meals for 5 days or at hospital discharge.

Adherence to treatment will be established as taking more than 95% of the NSS and not fasting for 2 consecutive days.

Item 19b: Description of how adherence to the intervention will be presented

The intervention will be applied by the research team, who will be responsible for the application and collection of data, which will be reported in daily formats in the morning and afternoon shifts.

The clinical investigators are going to prepare each supplement, administer, and witness each intake of the NSS, registering the time as well as any immediate side effects such as vomiting, bloating, and abdominal pain.

Item 19c: Definition of protocol deviation for the trial:

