Clinical Evolution	CG				IG				Intergroup p-value
	n	Baseline	Day 3	P value	n	Baseline	Day 3	P value	
Oxygen flow - L (intragroup)	40	5.9 ± 3.8	6 ± 4.4	0.919	40	6 ± 3.2	4.5 ± 3.5	0.014 *	
qSOFA - pts	40	0.42 ± 0.59	0.51 ± 0.57	0.608	40	0.65 ± 0.62	0.43 ± 0.49	0.040 *	
Number of defecations on day 3	37		0.81 ± 0.90		36		1.41 ± 1.13		0.014 *
Distension on day 3	31		51.60%		31		19.40%		0.008 *
PHO-9 test – pts (intragroup)	6	3.66 ± 2.5	1.50 ± 2.8	0.187	10	5.3 ± 3.4	1.9 ± 1.4	0.003 *	
Oxygen Saturation >90% on day 3 -%	40		85%		40		92.50%		0.241
Hydric Balance on day 3 - mL	17		123.4 ± 453.8		18		456.6 ± 485.5		0.043 *
Bristol scale on day 3 - %	24		33.30%		31		41.90%		0.356
40-day follow-up			Day 40				Day 40		
Saturation without Supplementary Oxygen - %	28		90.39 ± 3.4		38		92.08 ± 2.5		0.030 *
Need for home Oxygen flow - %	27		85.2%		39		66.70%		0.078
Time of home Oxygen use – days	17		57.6 ± 24.6		23		43.8 ± 16.2		0.098
Post-covid syndrome - %	24		37.50%		34		23.50%		0.195
Weight decrease - % of patients	11		72.70%		18		44.40%		0.135
Gastrointestinal symptoms - %	24		16.70%		37		8.10%		0.266

Table 2-A The following table shows the results of the intergroup analysis between the IG (Intervention Group) and the CG (Control Group) for different parameters in the baseline or with a complete 40-day follow-up. Deceased patients were excluded. * p-value <0.05.

Table 2-B. Association of baseline laboratory parameters and general mortality.

Baseline values	Discharge (n=72)		Death (n=8)		P value
	n	%	n	%	
Fibrinogen >700 mg/dL	13	18.50	6	75.00	0.002 *
Procalcitonin >0.5 ng/mL	4	5.5	4	50	0.003 *
Blood Urea Nitrogen >22 mg/dL	5	6.90	4	50	0.004 *
RCP >150 mg/L	28	38.8	7	87.5	0.011 *
Neutrophils >80%	45	62.50	8	100	0.031 *
Leucocytes >10 10 ³ /μL	18	25.00	5	62.50	0.040 *
Urea >40 mg/dL	12	16.6	4	50	0.047 *

Table 2-B. The results show the association between laboratory parameters taken in the baseline, with the overall mortality. Analysis was performed with Fisher's exact test. * p-value < 0.05.

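### SAP Item 26a plans a between-arm comparison of oxygen flow, qSOFA and PHQ-9, but the Section 27 table tests them only within each arm, so the NSS effect on them goes untested

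*SAP*

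**What the plan says.** Secondary objective 2 in SAP Item 8 is "To evaluate the effect of NSS on clinical and biochemical changes among patients".

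Item 26a, under secondary outcomes, lists oxygen flow, SpO2, "qSOFA scale, and gastrointestinal function will be assessed by comparing at baseline to day 3 intragroup and intergroup". The next sentence reads "The PHQ-9 test will be assessed at baseline and at discharge between both groups".

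Section 27 opens with "The analysis of the primary and secondary outcomes is shown in the following table". The table has 17 rows. Oxygen flow, qSOFA and PHQ-9 are given a paired t test or Wilcoxon test, marked as intragroup. The other 14 rows are marked as intergroup.

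Item 15 names only time points, for example "qSOFA scale: will be analyzed at baseline compared with day three", and does not settle which comparison is meant. Table 1-A compares oxygen flow and qSOFA between arms at baseline only. No other section supplies a between-arm follow-up test for the three outcomes.

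Two further rules bear on the reading of the results: Item 16 states "P values will be one-sided", and Item 28 states "Statistical methods to handle missing data will not be performed".

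**The concern.** The objective asks what NSS does. A within-arm change mixes any NSS effect with natural recovery, hospital treatment and regression to the mean. Only the comparison of randomised arms separates them, and for these three outcomes the table that governs the analysis leaves it out.

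Table 2-A shows the consequence. Its footnote presents it as an intergroup analysis, yet the intergroup cell is blank for all three outcomes while the intervention-arm changes carry stars. The oxygen-flow and PHQ-9 rows are at least labelled as intragroup; the qSOFA row is not. A reader will take a star in IG beside a non-significant CG p-value as evidence for NSS. Three of the seven starred results in that table are therefore not randomised comparisons.

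The same mismatch runs the other way on a smaller scale. Item 26a also plans an intragroup comparison for SpO2 and gastrointestinal function, but Section 27 gives the SpO2 >90% row and the gastrointestinal rows only a between-arm test at day 3.

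**Working it through.** **1. Plan against table**

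| Outcome | Item 26a | Section 27 | Table 2-A intergroup p |
|---|---|---|---|
| Oxygen flow | within and between arms | within only | blank |
| qSOFA | within and between arms | within only | blank |
| PHQ-9 | between arms | within only | blank |

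The between-arm comparison is planned for 3 of 3 outcomes and carried out for 0 of 3.

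**2. Inputs from Table 2-A** (mean ± SD, printed within-arm p)

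| | CG | IG |
|---|---|---|
| Oxygen flow, L (n 40/40) | 5.9 ± 3.8 to 6 ± 4.4, p 0.919 | 6 ± 3.2 to 4.5 ± 3.5, p 0.014 |
| qSOFA (n 40/40) | 0.42 ± 0.59 to 0.51 ± 0.57, p 0.608 | 0.65 ± 0.62 to 0.43 ± 0.49, p 0.040 |
| PHQ-9 (n 6/10) | 3.66 ± 2.5 to 1.50 ± 2.8, p 0.187 | 5.3 ± 3.4 to 1.9 ± 1.4, p 0.003 |

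The paired p-values cannot be reproduced, because the baseline/follow-up correlation is not printed. Of the printed p-values that can be checked, sidedness is mixed. Fisher 0.008 (16/31 v 6/31) and 0.241 (34/40 v 37/40) reproduce one-sided (two-sided 0.016 and 0.48). Hydric balance 0.043 is close to a two-sided t test (0.044).

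**3. Follow-up value between arms.** Welch test, CG minus IG, SE = √(s²_CG/n_CG + s²_IG/n_IG).
- Oxygen flow: 6 − 4.5 = 1.5; SE = √(4.4²/40 + 3.5²/40) = 0.889; 95% CI −0.3 to 3.3; two-sided p = 0.096, one-sided 0.048.
- qSOFA: 0.51 − 0.43 = 0.08; SE = 0.119; CI −0.16 to 0.32; two-sided p = 0.50.
- PHQ-9: 1.5 − 1.9 = −0.4; SE = 1.226; CI −3.3 to 2.5; two-sided p = 0.75.

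**4. Change score, SEs backed out of the printed p-values.** If those are two-sided paired t tests, the SE of change in an arm is |mean change| / t(p, n−1).
- Oxygen flow: SE 0.1/0.1024 = 0.977 (CG) and 1.5/2.573 = 0.583 (IG). Difference 0.1 + 1.5 = 1.6, SE = √(0.977² + 0.583²) = 1.138, CI −0.7 to 3.9, p = 0.16.
- qSOFA: SE 0.174 and 0.1035. Difference 0.09 + 0.22 = 0.31, SE 0.2025, CI −0.09 to 0.71, p = 0.13.
- PHQ-9: SE 1.413 and 0.845. Difference −2.16 + 3.40 = 1.24, SE 1.647, CI −2.5 to 5.0, p = 0.47.

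Rounding of the printed inputs alone gives p from 0.01 to 0.28 for oxygen flow (so uninformative), 0.11 to 0.15 for qSOFA and 0.43 to 0.51 for PHQ-9. The implied correlations, r = (s₀² + s₁² − s_d²)/(2s₀s₁), in CG/IG are −0.13/0.40, −0.80/0.32 and 0.15/0.67, so no single r can be inferred.

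**5. Assumed common r**, two-sided p for r = 0 / 0.2 / 0.4 / 0.6

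| | ANCOVA | Change score |
|---|---|---|
| Oxygen flow | 0.098 / 0.086 / 0.063 / 0.032 | 0.18 / 0.14 / 0.087 / 0.037 |
| qSOFA | 0.51 / 0.32 / 0.16 / 0.044 | 0.089 / 0.058 / 0.030 / 0.009 |
| PHQ-9 | 0.73 / 0.85 / 0.98 / 0.86 | 0.53 / 0.49 / 0.44 / 0.36 |

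For qSOFA this is only a sensitivity range, since the printed CG p (0.608) does not fit a positive r under a paired t test.

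**6. How often equal arms produce this pattern.** If both arms change equally and each paired test is significant with probability P, only IG is significant with probability P(1 − P). With no true change at one-sided 0.05 this is 0.05 × 0.95 ≈ 5%. When each paired test has 50% power it is 0.5 × 0.5 = 25%.

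**7. Consistency of the qSOFA inputs.** Scores are integers. A CG day-3 mean of 0.51 cannot arise from 40 patients (20/40 = 0.500, 21/40 = 0.525); 20/39, 19/37 and 18/35 all fit. With n = 39 the Welch p is 0.51 and the change-score p stays 0.13. In IG, a mean of 17/40 = 0.425 needs a sample SD of at least √[(17 − 17²/40)/39] = 0.501, so the printed 0.49 does not fit either.

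**The case against.** The strongest reply is that the between-arm comparison is in the plan, in Item 26a, so this is an inconsistency and not an omitted analysis. That is fair as a description of the SAP as a whole. It does not help, because Section 27 is the part that assigns the tests, and Table 2-A shows that it was the part followed.

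Second, the illustrative figures are fragile. They assume normality, whereas Section 27 switches to Wilcoxon when data are not normal, which is likely for qSOFA. The printed qSOFA summaries do not fit n = 40. The Table 2-A footnote also says that the deceased were excluded, while Figure 2 reports seven CG deaths and one IG death and the oxygen-flow row still prints 40 and 40. If the exclusion applied at day 3 (33 v 39, same means and SDs), the oxygen-flow Welch p would be 0.119 two-sided and 0.060 one-sided. All of this stands, and it is why the figures serve as illustration only.

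Third, on the SAP's one-sided rule the oxygen-flow follow-up comparison (0.048) would count as significant, as would its whole ANCOVA range when halved (0.049 to 0.016). That also stands. NSS may have changed oxygen flow; the point is that the planned test of it was not reported.

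Fourth, baseline adjustment appears nowhere in the SAP, and results are already printed. The answer is to report the SAP's own unpaired method as well and to disclose when the adjusted model was chosen.

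**Conclusion.** The contradiction holds and can be read directly from Item 26a and Section 27. Following Section 27 leaves secondary objective 2 unanswered for oxygen flow, qSOFA and PHQ-9, and three of the seven stars in Table 2-A rest on within-arm tests.

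The printed summaries cannot show whether NSS changed these outcomes. For oxygen flow and qSOFA the between-arm answer depends on the model, on the sidedness and on a correlation that is not given. PHQ-9 stays far from significance in every version tried (two-sided p 0.36 or more), but it covers only 6 + 10 = 16 of 80 patients and is too imprecise to conclude either way. The between-arm figures assume normality and the printed means, SDs and numbers.

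This should be fixed. It touches secondary outcomes only; the primary log-rank tests are unaffected.

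**What to change.** Reconcile Item 26a with Section 27:

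1. Give oxygen flow, qSOFA and PHQ-9 a between-arm analysis: the follow-up value compared between arms, adjusted for baseline, with the difference and its 95% CI. Use a rank-based or ordinal method for qSOFA, and for any outcome that is not normal.
2. Report beside it the unadjusted unpaired t or Mann-Whitney comparison, which is the SAP's own intergroup method. Disclose that the adjusted model was chosen after results were seen, and that the intergroup comparison itself was already planned in Item 26a.
3. Fill the three blank intergroup cells of Table 2-A and state whether each p-value is one- or two-sided. Give the actual qSOFA day-3 numbers and SDs in both arms, and say whether the exclusion of deceased patients applies at day 3.
4. Keep the within-arm changes as description, without stars.
5. Mark PHQ-9 as a complete-case comparison of 16 of 80 patients.
6. Either add or delete the intragroup comparison that Item 26a plans for SpO2 and the gastrointestinal items.

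The cost is a few lines of SAP text and three re-analyses of data already held. Some stars may be lost, and the PHQ-9 comparison will stay imprecise.
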